### 13.1. Drug Concentration Measures

Drug concentration-time data will be listed for each subject.

### 13.2. Deriving and Summarizing Pharmacokinetic Parameters

For subjects in the active treatment group, the pharmacokinetic parameters will be determined directly from the concentration-time data and will be extracted from the pharmacokinetic concentration file by CPMS GSK.

For the calculation of individual pharmacokinetic profiles, if one or more non-quantifiable (NQ) values occur in a profile before the first measurable concentration, they will be assigned a value of zero concentration. If a single NQ value occurs between measurable concentrations in a profile, the NQ should generally be omitted (set to missing) in the derivation of pharmacokinetic parameters. If two or more NQ values occur in succession between measurable concentrations, these NQs and any subsequent measurable concentrations will be omitted (set to missing) for the derivation of pharmacokinetic parameters.

NQs which occur after the last measurable concentration will be omitted (set to missing) in the derivation of pharmacokinetic parameters.

The following PK parameters will be determined if data permit:

- maximum observed concentration ( $C_{max}$ )
- time to  $C_{max}$  ( $t_{max}$ )
- area under the plasma concentration-time curve ( $AUC(0-t)$ ,  $AUC(0-\infty)$  (Week1 Day1 only),  $AUC(0-\tau)$ )
- apparent terminal phase half-life ( $t_{1/2}$ )
- Trough concentration ( $C_{\tau}$ )
- The observed accumulation ratio ( $R_o$ )

The ratio of  $AUC(0-\tau)$  on Week 3 Day 4 / Week 1 Day 1  $AUC(0-\tau)$  will be calculated to assess time invariance.

- Clearance ( $CL/F$ ) and Volume of distribution ( $V_z/F$ )

All derived PK parameters will be listed.

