#### 4.2.2. Accelerated Dose Escalation

One subject per dose level in the accelerated dose escalation phase will be treated to minimize suboptimal drug exposures, starting with Dose Level 1 and will continue until one subject experiences  $\geq$  Grade 2 drug related toxicity (based on National Cancer Institute- Common Terminology Criteria for Adverse Events, Version 4 (NCI-CTCAE v4.03 [NCI-CTCAE, 2010]) or dose-limiting toxicity (DLT, see Section 4.2.4). The accelerated dose titration scheme is described in Table 1. A single dose (Day 1) will be given to subjects in each cohort with the collection of blood samples for PK analysis at timed intervals. Once the final PK sample for Day 1 is obtained, subjects may begin repeat dosing on Day 3. The dose for Dose Level 2 and subsequent cohorts will be based on the pharmacokinetics (PK) and safety analysis of the previous cohort. Inter-subject variability in exposure and toxicity will also be considered when deciding on actual doses administered during dose-escalation. Dose escalation will occur according to the procedures outlined in Table 1.

A sufficient number of subjects will be enrolled in each cohort to ensure that data from at least one subject that has completed a full treatment cycle (4 weeks) of dosing is available prior to defining a new dose and starting the next cohort. The dose-escalation decision and rationale for the subsequent cohort(s) will be documented in writing with copies maintained at each study site and in the master study files at GlaxoSmithKline (GSK).

At the first occurrence of a DLT (refer to Section 4.2.4) or any Grade 2 toxicity based on NCI-CTCAE v4.03 (with the exception of Grade 2 alopecia, nausea, vomiting, diarrhea, hemoglobin, lymphopenia, taste changes or alkaline phosphatase in the presence of bony metastases) during the first 4 weeks, the Accelerated Dose Titration phase will be terminated and the ongoing cohort will be expanded up to 6 subjects to commence the 3 + 3 Dose-Escalation phase of the study.

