## 8.4. Pharmacokinetics

PK analyses will be the responsibility of GSK Clinical Pharmacokinetics Modeling & Simulation (CPMS). Plasma GSK2820151 concentration-time data will be analyzed by non-compartmental methods with WinNonlin.

From the plasma concentration-time data, the following pharmacology parameters will be determined, as data permit: maximum observed plasma concentration ( $C_{max}$ ), time to  $C_{max}$  ( $t_{max}$ ), area under the plasma concentration-time curve ( $AUC_{(0-\tau)}$  and  $AUC_{(0-\infty)}$  Week 1 Day 1 only) and apparent terminal phase half-life ( $t_{1/2}$ ). Trough concentration ( $C_{\tau}$ ) samples collected on the specified days will be used to assess attainment of steady state. To estimate the extent of accumulation after repeat dosing, the observed accumulation ratio ( $R_o$ ) may be determined from the ratio of  $AUC_{(0-\tau)}$  in Week 3 Day 4 /  $AUC_{(0-\tau)}$  in Week 1 Day 1. The ratio of  $AUC_{(0-\tau)}$  on Week 3 Day 4/ Week 1 Day 1  $AUC_{(0-\infty)}$  will be calculated to assess time invariance. GSK2820151 concentrations will be determined in urine samples to determine urinary recovery of unchanged drug and renal clearance.

Plasma concentration-time data will be listed by dose and summarized using descriptive statistics (n, mean, standard deviation [SD], median, minimum and maximum) by planned relative assessment time. Mean and/ or median values will be plotted over time. Individual plasma and urinary (if available) PK parameters values as well as a descriptive summary (mean, standard deviation, median, minimum, maximum, geometric mean, and the standard deviation, CV% and 95% confidence interval of log-transformed parameters [if applicable]) by dose cohort will be reported.

Cmax and AUC (AUC(0-∞), single dose, and AUC(0-τ), steady state) will be plotted as a function of the dose administered. If more than 2 dose cohorts are evaluated, dose proportionality of AUC and Cmax for GSK2820151 will be assessed using the power model (details will be provided in the Reporting and Analysis Plan [RAP]).

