## 11.4. Data Analysis Considerations

Data will be listed and summarized according to GSK reporting standards, where applicable. Complete details will be documented in the RAP. Any deviations from, or additions to, the original analysis plan described in this protocol will be documented in the RAP and final study report.

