## 2. SUMMARY OF KEY PROTOCOL INFORMATION

### 2.1. Changes to the Protocol Defined Statistical Analysis Plan

Protocol Section	Change from Protocol	Rationale
Section 11.4.2 Interim Analysis	No interim analysis in SAP	Sponsor made the decision to terminate the study early and no interim analysis needed
Section 11.2 Continual Reassessment Method	No N-CRM analysis in SAP	Sponsor made the decision to terminate the study early and did not get into N-CRM analysis phase
Section 11 Statistical Considerations and Data Analyses	No summary tables and figures No statistical analysis of pharmacokinetic parameters	Sponsor made the decision to terminate the study early and no tables/figures needed, only listings provided
Section 8.3.9 Clinical Safety Laboratory Assessments	No Creatinine Phosphokinase	This test was not collected per CRF
Section 11.5.3 Other Analyses	No biomarker, pharmacodynamics exploratory analyses performed	Sponsor made decision that biomarkers samples were not collected after 11Jan2018 and the biomarker samples collected by 11Jan2018 were destroyed.

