xxx/ xxxxxx	xx.xx	xx.xx	xx.xx	xx.xx	xx.xx	xx.xx	xx.xx	xx.xx	xx.xx	xx.xx

[1] Ratio of AUC(0-tau): AUC(0-tau) on Week 3 Day 4/AUC(0-tau) on Week 1 Day 1

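### SAP 13.2 assesses time invariance with the ratio that Protocol 8.4 defines as the accumulation ratio, and does not declare the change of denominator (minor impact)

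*SAP*

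**What the plan says.** Protocol 8.4 sets out two ratios with two purposes. For accumulation, Ro "may be determined from the ratio of" AUC(0-τ) in Week 3 Day 4 to AUC(0-τ) in Week 1 Day 1. For time invariance, the numerator is the same but the denominator is the Week 1 Day 1 AUC(0-∞). Protocol 11.5.2.1.1 repeats the time-invariance ratio. Its numerator wording is garbled, but the AUC(0-∞) denominator is clear.

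SAP 13.2 names Ro as a parameter without labelling any formula as its own. It then states that AUC(0-τ) on Week 3 Day 4 over Week 1 Day 1 AUC(0-τ) "will be calculated to assess time invariance". Footnote [1] of the derived PK parameter listing at the end of the SAP reads "Ratio of AUC(0-tau): AUC(0-tau) on Week 3 Day 4/AUC(0-tau) on Week 1 Day 1".

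On documentation, Protocol 11.4 says: "Any deviations from, or additions to, the original analysis plan described in this protocol will be documented in the RAP and final study report". In SAP 2.1 the only entry on PK is "No statistical analysis of pharmacokinetic parameters". The ratio survives that entry, because SAP 13.2 still derives the parameters and says "All derived PK parameters will be listed".

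**The concern.** The SAP attaches the purpose of one protocol ratio to the formula of the other. The two have different reference values. With linear kinetics that do not change over time, steady-state AUC over a dosing interval equals single-dose AUC to infinity, so the protocol ratio is 1 and a departure from 1 suggests time-dependent kinetics. Day 1 AUC(0-τ) leaves out whatever exposure follows the first 24 h. The SAP ratio is therefore above 1 whenever any drug carries over, even if clearance never changes. A reader who takes a value above 1 as evidence against time invariance may be looking only at accumulation. The change also cannot be traced from SAP 2.1, and nothing in the documents shows whether it is a drafting slip or a decision.

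**Working it through.** **1. The definitions side by side**

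| Quantity | Protocol 8.4 | SAP 13.2 |
|---|---|---|
| Ro | AUC(0-τ) W3D4 / AUC(0-τ) W1D1 | named, no formula labelled as Ro |
| Time invariance | AUC(0-τ) W3D4 / AUC(0-∞) W1D1 | AUC(0-τ) W3D4 / AUC(0-τ) W1D1 |

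The SAP's time-invariance ratio is the protocol's Ro.

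**2. Inputs**

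- Clearance 6.5 mL/min/kg, volume 2.8 L/kg and half-life about 5 h, all predicted (Protocol 4.5.1). Check: 6.5 × 60 / 1000 = 0.39 L/h/kg, and ln 2 × 2.8 / 0.39 = 4.98 h, which reproduces the stated half-life.
- τ = 24 h. Doses fall on study days 1, 3–5, 8–12 and daily from day 15 (Protocol 6.1). Week 3 Day 4 is study day 2 × 7 + 4 = 18.
- The documents give no observed half-life. Values of 8, 12 and 24 h are assumptions to show the range.

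**3. Steady-state formula** (one compartment, instantaneous input, time-invariant kinetics)

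Set single-dose AUC(0-∞) = 1. Day 1 AUC(0-τ) is then 1 − 2^(−24/t½), and steady-state AUC(0-τ) is 1. So:

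- protocol ratio = 1 / 1 = 1
- SAP ratio = 1 / (1 − 2^(−24/t½))

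At 5 h, 2^(−4.8) = 0.036, so the SAP ratio is 1 / 0.964 = 1.037. It reaches 1.10 when 2^(−24/t½) = 1/11, which is a half-life of 6.94 h.

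**4. Actual dosing days**

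For dosing days d up to 18, the SAP ratio is the sum of 2^(−24(18−d)/t½). The protocol ratio is that sum times (1 − 2^(−24/t½)).

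| Half-life | SAP ratio | Protocol ratio |
|---|---|---|
| 5 h (predicted) | 1.037 | 1.000 |
| 8 h (assumed) | 1.143 | 1.000 |
| 12 h (assumed) | 1.328 | 0.996 |
| 24 h (assumed) | 1.905 | 0.953 |

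The protocol ratio falls slightly below 1 at long half-lives because steady state is not fully reached by day 18.

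**5. Sensitivity to absorption and sampling**

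With first-order absorption (assumed ka = 1/h) and trapezoidal AUCs at the sampling times in Protocol Tables 9 and 10, the SAP ratio is 1.044, 1.160 and 1.358 at 5, 8 and 12 h. The protocol ratio is 1.000, 1.000 and 0.996. The pattern does not depend on the instantaneous-input simplification.

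**6. Can the protocol ratio still be formed?**

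Yes. SAP 13.2 derives Day 1 AUC(0-∞) ("Week1 Day1 only"). Protocol 4.2.2 says "Once the final PK sample for Day 1 is obtained, subjects may begin repeat dosing on Day 3", and Protocol 6.1 schedules no Day 2 dose, so the Day 1 profile is a single-dose profile.

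**The case against.** The strongest objection is about weight. Only listings are produced, for five subjects. No test, cut-off or decision uses the ratio. A reader could form the protocol ratio from the listed AUCs where data permit. At the only documented half-life the offset is under 4%, and the larger gaps rest on assumed half-lives. All of this stands, and it is why the impact is called minor.

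A second objection is about layout. In SAP 13.2 the ratio sentence comes directly after the Ro item and interrupts the list, so it could be read as the Ro formula with a misplaced purpose phrase. That is possible. On that reading the stated purpose is still wrong, and the protocol's time-invariance ratio has been dropped without being declared. Protocol 8.4 words Ro as optional, but the formula there is the only one it gives.

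Third, Protocol 11.4 does not say which RAP section must record deviations, and the study report is not available here. The omission from SAP 2.1 is therefore a traceability gap rather than a proven breach. Finally, the listing footnote states its formula openly and does not mention time invariance. Its column heading is not in the text available, so no labelling error is claimed there.

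**Conclusion.** The concern holds. SAP 13.2 gives a formula that does not serve its stated purpose, the formula differs from the one in Protocol 8.4 and 11.5.2.1.1, and SAP 2.1 does not declare the difference. Under time-invariant kinetics the mislabelled ratio exceeds its intended reference value of 1 by about 4% at the predicted half-life of about 5 h. The excess passes 10% if the true half-life is above about 6.9 h. These figures assume linear one-compartment kinetics and the planned once-daily schedule, and the longer half-lives are assumptions. No planned conclusion changes. This corrects a stated rule and should be made, but it is a small point.

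**What to change.** In SAP 13.2, define the time-invariance ratio as AUC(0-τ) on Week 3 Day 4 over AUC(0-∞) on Week 1 Day 1, and list it. Give Ro the formula AUC(0-τ) on Week 3 Day 4 over AUC(0-τ) on Week 1 Day 1. If the AUC(0-τ) denominator is intended, add a row to SAP 2.1 saying so and delete the time-invariance purpose from the sentence in 13.2. Either way, check that the listing column tied to footnote [1] agrees with the definition chosen.

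The cost is two formula lines and one extra quotient per subject, with no new data. One trade-off is that Day 1 AUC(0-∞) relies on extrapolation beyond the last planned sample at 33 h. The extrapolated share is 2^(−33/t½): about 1% at 5 h, and about 6% and 15% at the assumed 8 h and 12 h. Listing that percentage would help a reader but is optional.

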#### **14. PHARMACOGENETIC DATA ANALYSES**

Further details on PGx analyses discussed in the protocol may be identified/addressed in a separate RAP, if applicable.

**16. APPENDIX 1: LIST OF DATA DISPLAYS**

**16.1. Data Display Numbering**

The following numbering will be applied for RAP generated displays:

Section	Listings
ICH Listings	1 to 46
Non-ICH Listings	47 to 53

**16.2. Deliverable**

Delivery	Description
SAC	Final Statistical Analysis Complete

**16.3. ICH Listings**

No.	Population	Title	Programming Notes	Deliverable
Subject Disposition				
1.	All Treated	Listing of Subject Consent	ICH E3	SAC
2.	All Treated	Listing of Scheduled and Actual Treatment	ICH E3	SAC
3.	All Treated	Listing of Reasons for Study Withdrawal	ICH E3	SAC
4.	All Treated	Listing of GSK2820151 Treatment Discontinuations	ICH E3	SAC
Protocol Deviations				
5.	All Treated	Listing of Subjects with Inclusion/Exclusion Criteria Deviations	ICH E3	SAC
6.	All Treated	Listing of Protocol Deviations		
Demographic and Baseline Characteristics				
7.	All Treated	Listing of Demographic Characteristics	ICH E3	SAC
8.	All Treated	Listing of Race	ICH E3	SAC
9.	All Treated	Listing of Family History	ICH E3	SAC
10.	All Treated	Listing of Medical Conditions	ICH E3	SAC
11.	All Treated	Listing of Disease Characteristics at Initial Diagnosis	ICH E3	SAC
12.	All Treated	Listing of Disease Characteristics at Screening	ICH E3	SAC
Prior and Concomitant Medications				
13.	All Treated	Listing of Prior Anti-Cancer Therapy	Study specific	SAC
14.	All Treated	Listing of Prior Anti-Cancer Radiotherapy	Study specific	SAC

No.	Population	Title	Programming Notes	Deliverable
15.	All Treated	Listing of Prior Cancer and Non-Cancer Related Surgical Procedures	Study specific	SAC
16.	All Treated	Listing of Concomitant Medications	ICH E3	SAC
17.	All Treated	Listing of Blood Products and Blood Supportive Care Products	Study specific	SAC
18.	All Treated	Listing of Follow-Up Anti-Cancer Therapy	Study specific	SAC
19.	All Treated	Listing of Follow-Up Surgical Procedures	Study specific	SAC
Exposure and Treatment Compliance				
20.	All Treated	Listing of Exposure to GSK2820151	ICH E3	SAC
21.	All Treated	Listing of Dose Interruptions	ICH E3	SAC
22.	All Treated	Listing of Dose Reductions	ICH E3	SAC
Adverse Events				
23.	All Treated	Listing of Adverse Events Profiles	ICH E3	SAC
Serious and Other Significant Adverse Events				
24.	All Treated	Listing of Fatal Serious Adverse Events	ICH E3	SAC
25.	All Treated	Listing of Non-Fatal Serious Adverse Events	ICH E3	SAC
26.	All Treated	Listing of Adverse Events Leading to Discontinuations of GSK2820151 Treatment Profiles	ICH E3	SAC
27.	All Treated	Listing of Adverse Events Leading to Dose Interruptions	ICH E3	SAC
28.	All Treated	Listing of Adverse Events Leading to Dose Reductions	ICH E3	SAC
29.	All Treated	Listing of Adverse Events Recorded as Dose-Limiting Toxicities	Study specific	SAC
30.	All Treated	Listing of Adverse Events of Special Interest	Study specific	SAC
31.	All Treated	Listing of Deaths	ICH E3	SAC
32.	All Treated	Listing of Subject Numbers for Specific Causes of Deaths	ICH E3	SAC
All Laboratory				
33.	All Treated	Listing of Clinical Chemistry Data	ICH E3	SAC
34.	All Treated	Listing of Hematology Data	ICH E3	SAC
35.	All Treated	Listing of Thyroid Function Test Data	ICH E3	SAC
36.	All Treated	Listing of Urinalysis Data	ICH E3	SAC
37.	All Treated	Listing of Coagulation Data	ICH E3	SAC

No.	Population	Title	Programming Notes	Deliverable
38.	All Treated	Listing of Pancreatic Markers Data	ICH E3	SAC
39.	All Treated	Listing of Lipid Panel Data	ICH E3	SAC
40.	All Treated	Listing of Serum Data	ICH E3	SAC
Vital Signs				
41.	All Treated	Listing of Vital Signs	ICH E3	SAC
ECOG				
42.	All Treated	Listing of ECOG Performance Status Scale	ICH E3	SAC
ECG and LVEF				
43.	All Treated	Listing of Abnormal ECG Findings	ICH E3	SAC
44.	All Treated	Listing of ECG Values	ICH E3	SAC
45.	All Treated	Listing of Change from Baseline ECG Values	ICH E3	SAC
46.	All Treated	Listing of Left Ventricular Ejection Fraction (LVEF) ECHO Results	ICH E3	SAC

**16.4. Non-ICH Listings**

No.	Population	Title	Programming Notes	Deliverable
Efficacy Endpoints				
47.	All Treated	Listing of Investigator-Assessed Response (RECIST 1.1)	Study specific	SAC
48.	All Treated	Listing of Investigator-Assessed Target Lesions (RECIST 1.1)	Study specific	SAC
49.	All Treated	Listing of Investigator-Assessed Non-Target Lesions (RECIST 1.1)	Study specific	SAC
50.	All Treated	Listing of Investigator-Assessed New Lesions	Study specific	SAC
51.	All Treated	Listing of Progression Free Survival (RECIST 1.1)	Study specific	

No.	Population	Title	Programming Notes	Deliverable
Pharmacokinetic				
52.	PK Population	Listing of GSK2820151 Pharmacokinetic Concentration-Time Data	ICH E3	SAC
53.	PK Population	Listing of Derived GSK2820151 Pharmacokinetic Parameters	ICH E3	SAC

Protocol: GSK201893  
Population: All Treated

Listing 1  
Listing of Subject Consent

Country: xxxxxx  
Investigator: xxxxx xxxxxx

Center/ Subject ID	Original Informed Consent			Reconsented			Pharmacogenetic Research Consent		
	Date	Consent Version	Protocol Version	Date	Consent Version	Protocol Version	Date	Reason	Date of Withdrawal
xxxx/ xxxxxx	ddMMyyyy	xxx	xxx	ddMMyyyy	xxx	xxx	ddMMyyyy		
xxxx/ xxxxxx	ddMMyyyy	xxx	xxx	ddMMyyyy	xxx	xxx		xxx	
xxxx/ xxxxxx	ddMMyyyy	xxx	xxx	ddMMyyyy	xxx	xxx	ddMMyyyy		ddMMyyyy

Protocol: GSK201893  
Population: All Treated

Listing 2  
Listing of Scheduled and Actual Treatment

Country: xxxxxx  
Center: XXXX  
Investigator: xxxxxx xxxxxx

Subject ID	Planned Treatment	Actual Treatment
xxxx	3 mg	3 mg
	6 mg	6 mg

Protocol: GSK201893  
Population: All Treated

Listing 3  
Listing of Reasons for Study Withdrawal

Treatment = GSK2820151 xxx mg

Center/ Subject ID	Date of Withdrawal	Study Day	Primary Reason	Subreason
xxxx/ xxxxxx	ddMMyyyy	x	Study closed/terminated	
xxxx/ xxxxxx	ddMMyyyy	x	Lost to Follow-up	
xxxx/ xxxxxx	ddMMyyyy	xx	Investigator discretion	
...				

Protocol: GSK201893  
Population: All Treated

Listing 4  
Listing of GSK2820151 Treatment Discontinuations

Treatment = xxxxxx

Center/ Subject ID	Cumulative Dose (mg)	Date of Last Dose	Study Day	Primary Reason for Treatment Discontinuation
xxxxx/ xxxxxx	xxx	ddMMyyyy	xx	xxxxxxxxxxxxxxxxxxxx
xxxxx/ xxxxxx	xxx	ddMMyyyy	xx	xxxxxxxxxxxxxxxxxxxx
xxxxx/ xxxxxx	xxx	ddMMyyyy	xx	xxxxxxxxxxxxxxxxxxxx
xxxxx/ xxxxxx	xxx	ddMMyyyy	xx	Xxxxxxxxxxxxxxxxxxxx

Protocol: GSK201893  
Population: All Treated

Listing 6  
Listing of Protocol Deviations

Treatment = xxxxxx

Center/ Subject ID	Date of Deviation/ Study day	Category	Description
xxxxxx/ xxxxxx	ddMMMyyyy/ xx	Prohibited medication or device	xxxxxxxxxxxxxx
	ddMMMyyyy/ xx	Assessments and/or procedures/ Study treatment supply procedure	xxxxxxxxxxxxxx
xxxxxx/ xxxxxx	ddMMMyyyy/ xx	Eligibility criteria not met	xxxxxxx
xxxxx/ xxxxxx	ddMMMyyyy/ xx	Not withdrawn after developing withdrawal criteria/ Not discontinued from study treatment	xxxxxxx

Protocol: GSK201893  
Population: All Treated

Listing 7  
Listing of Demographic Characteristics

Treatment = xxxxxx

Center/ Subject ID	Year of Birth[1]	Age (Years)	Sex	Child-bearing Potential	Ethnicity	Height (cm)	Weight (kg)	BMI (kg/m  )
xxxxx/ xxxxxx	xxxx	xx	F	Pre-menarcheal	Hispanic or Latino	xxx.x	xx.x	xx.x
xxxxx/ xxxxxx	xxxx	xx	F	xxxxxxxxxxxxxx	Not Hispanic or Latino	xxx.x	xx.x	xx.x
xxxxx/ xxxxxx	xxxx	xx	M		Not Hispanic or Latino	xxx.x	xx.x	xx.x

[1] For calculating age, birthdate is imputed as June 30 in the year of birth.

Protocol: GSK201893  
Population: All Treated

Listing 8  
Listing of Race

Treatment = xxxxxx

Center/ Subject ID	Race
xxxxx/ xxxxxx	African American/African Heritage Asian - East Asian Heritage
xxxxx/ xxxxxx	White - White/Caucasian/European Heritage
xxxxx/ xxxxxx	African American/African Heritage

---

Protocol: GSK201893  
Population: All Treated

Listing 9  
Listing of Family History

Treatment = xxxxxx

Center/ Subject ID      A family history of premature coronary artery disease in women <65 yrs or  
men <55 years in first degree relatives only?

---

xxxxx/                      Yes  
xxxxxx  
xxxxx/                      No  
xxxxxx

---

Protocol: GSK201893  
Population: All Treated

Listing 10  
Listing of Medical Conditions

Treatment = xxxxxx

Center/ Subject ID	Category	Medical Condition	Status	NCI CTCAE Grade	Classification	
xxxxx/ xxxxxx	Cardiovascular Risk Factors	ANGINA PECTORIS	Current		xxxxx	
		DIABETES	Past		xxxxx	
		HYPERTENSION	Current	x	xxxxx	
			Current		xxxxxxxxxxxx	
	Other medical condition	xxxxx	Not assessed			
			Current			xxxx
		xxxxxxxx	Past			xxxx
		xxxxxxxx	Current	x		xxxx

NCI-CTCAE version 4.03

Programming note: As coding is not done for medical conditions in SDTM MH, please display MHTERM as verbatim term as in other AE listings.

Protocol: GSK201893  
Population: All Treated

Listing 11  
Listing of Disease Characteristics at Initial Diagnosis

Treatment = xxxxxx

Center/ Subject ID	Primary Tumor Type	Date of Diagnosis/ Time Since Diagnosis (Months)	Histology of Tumor	Histological Grade	Primary Tumor HPV Status
xxxx/ xxxxxx	Bladder	ddMMMyyyy/10.2	xxxx	Well differentiated	Negative
xxxx/ xxxxxx	Xxxx	ddMMMyyyy/xxx.x	xxxx	xxx	xxxxxxxxx

Protocol: GSK201893  
Population: All Treated

Listing 12  
Listing of Disease Characteristics at Screening

Treatment = xxxxxx

Center/ Subject ID	Measurable Disease	Non Target Lesions	Stage	Progress on Therapy?	Date of Last Recurrence/Time from Last Recurrence (Months)	Metastatic/ Unresectable Disease	Number of Previous Radiotherapy Regimens
xxxx/ xxxxxx	Yes	Yes	III	YES	ddMMMyyyy/xx.x	Yes	2
xxxx/ xxxxxx	..	..	IIIA	NO	ddMMMyyyy/x.x	XXX	1

Protocol: GSK201893  
Population: All Treated

Listing 13  
Listing of Prior Anti-Cancer Therapy

Treatment = xxxxxx

Center/ Subject ID	ATC Level 1/ Preferred Term/ Verbatim Text	Regimen Sequence/ Type [1]	Intent	Start Date/ Study Day/ Stop Date/ Study Day	Duration of Therapy (Days)	Small Molecule Targeted Therapy Type
xxxx/ xxxxxx	Endocrine & metabolic/ Cytosol/ CYTOXAN	1/ C	Neo-Adjuvant	ddMMMyyyy/ xxx/ ddMMMyyyy/ xxx	xxx	AKT Inhibitor
	xxxxxxxxxx/ xxxxxxxxxx/ XXXXXXXX	x/ H	Induction	ddMMMyyyy/ xxx/ ddMMMyyyy/ xxx	xxx	

[1]Therapy Type: C=Chemotherapy, H=Hormonal Therapy, I=Immunotherapy, B=Biologic Therapy.

Protocol: GSK201893  
Population: All Treated

Listing 14  
Listing of Prior Anti-Cancer Radiotherapy

Treatment = xxxxxx

Center/ Subject ID	Body Site	Cumulative Dose (unit)/ Intent	Start Date/ Study Day/ Stop Date/ Study Day	Duration of Therapy (Days)
xxxxxx/ xxxxxx	RIGHT UPPER LOBE LUNG	xxx (xxxx)/ Local/Regional	ddMMMyyyy/ xxx/ ddMMMyyyy/ xxx	xxx
xxxxxx/ xxxxxx	CHEST	xxx (xxxx)/ Palliative	ddMMMyyyy/ xxx/ ddMMMyyyy/ xxx	xxx
xxxxxx/ xxxxxx	COLON	xxx (xxxx)/ Local/Regional	ddMMMyyyy/ xxx/ ddMMMyyyy/ xxx	xx
xxxxxx/ xxxxxx	COLON	xxx (xxxx)/ Local/Regional	ddMMMyyyy/ xxx/ ddMMMyyyy/ xxx	xx

Protocol: GSK201893  
Population: All Treated

Listing 15  
Listing of Prior Cancer and Non-Cancer Related Surgical Procedures

Treatment = xxxxxx

Center	Subject	Classification	Date of Procedure	Study Day	Verbatim Term
xxxxx	xxxx	Cancer related	ddMMMyyyy	-xx	
		Cancer related	ddMMMyyyy	xx	
	xxxx	Cancer related	ddMMMyyyy	xx	
xxxxx	xxxx	Cancer related	ddMMMyyyy	-xx	
		Other general	ddMMMyyyy	xxx	Hysterectomy

Protocol: GSK201893  
Population: All Treated

Listing 16  
Listing of Concomitant Medications

Treatment = xxxxxx

Center/ Subject ID	ATC Level 1/ Ingredient/ Verbatim Text	Dose/ Units/ Freq/ Route	Date Started/ Study Day	Date Stopped/ Study Day	Medication Category	Reason For Medication
xxxxx/ xxxxxx	Fluticasone propionate/ FLIXOTIDE/ Asthma	xx/ MG/ 2XD/ IH	ddMMMyyyy/ xx	ddMMMyyyy/ xx	General Concomitant Medication	xxxxx
xxxxx/ xxxxxx	XXXXXXXXXXXX/ xxxxxxx	xxx/ xxx/ xxxx/ xx	ddMMMyyyy/ xx	ddMMMyyyy/ xx	Concomitant Medication of Interest /Suspected in causing SAE	xxxxx

Protocol: GSK201893  
 Population: All Treated

Listing 17  
 Listing of Blood Products and Blood Supportive Care Products

Treatment = xxxxx

Center/ For SF, was  
 Subject it admin-  
 ID istered?

ID	Product	Product Type	Date	Quantity or Dose	Unit	Frequency
xxxxx/ xxxxxx	Blood products	Red Blood Cells	ddMMMyyyy	xxx		
		Platelets	ddMMMyyyy	xxx		
		Whole Blood	ddMMMyyyy	xxx		
		Plasma - FFP	ddMMMyyyy	xxx		
		Cryoprecipitate	ddMMMyyyy	xxx		
		White Blood Cells	ddMMMyyyy	xxx		
		Other Blood Product, specify	ddMMMyyyy	xxx		
...	Blood supportive care products	darbepoetin alfa (Aranesp)	ddMMMyyyy	xxx		
		eltrombopag (i.e. Promacta)	ddMMMyyyy	xxx		
		pegfilgrastim (NeulastaR)	ddMMMyyyy	xxx		
		romiplostim (i.e. NPlate)	ddMMMyyyy	xxx		

SF: stimulating Factor; P = Prophylactically; A = As treatment.

Protocol: GSK201893  
Population: All Treated

Listing 18  
Listing of Follow-Up Anti-Cancer Therapy

Treatment = xxxxxx

Center/ Subject ID	Best Response	Time to Progression (Days)	ATC Level 1/ Preferred Term/ Verbatim Text	Start Date/ Study Day/ Stop Date/ Study Day	Duration of Therapy	Type of Therapy	Reason for Stopping Therapy
xxxx/ xxxxxx	Progressive disease	xxx	Endocrine & metabolic/ Cytosan/ CYTOXAN	ddMMyyyy/ xxx/ ddMMyyyy/ -xxx	xxx d	Chemotherapy	xxxxx
			xxxxxxxx/ xxxxxxxxxx/ XXXXXXXXXX	ddMMyyyy/ xxx/ ddMMyyyy/ -xxx	xxx d	Hormonal	xxxxx
			xxxxxxxx/ xxxxxxxxxx/ XXXXXXXXXX	ddMMyyyy/ xxx/ ddMMyyyy/ -xxx	xxx d	Radiation	xxxxxxxxxx

Note: Follow-up surgeries are listed separately.

Protocol: GSK201893  
Population: All Treated

Listing 19  
Listing of Follow-Up Surgical Procedures

Treatment = xxxxxx

Center/ Subject ID	Classification	Date of Procedure	Study Day	Verbatim Term
xxxxxx/ xxxxxx	Cancer related	ddMMyyyy	xx	
	Cancer related	ddMMyyyy	xx	
xxxxxx/ xxxxxx	Cancer related	ddMMyyyy	xx	
	Other surgical procedures	ddMMyyyy	xxx	Hysterectomy

Protocol: GSK201893  
Population: All Treated

Listing 20  
Listing of Exposure to GSK2820151

Treatment = xxxxxx

Center/ Subject ID	Average Daily Dose	Start Date/ Study Day	Stop Date/ Study Day	Dose (mg)	Cumulative Dose (mg)
xxxx/ xxxxxx	xxxx	ddMMyyyy xx	xx/ xx	xx	xx

---

Average daily dose is defined as the cumulative dose divided by the duration of exposure for each subject in days.  
The cumulative dose is the sum of the doses administered for a subject.

Note: Average Daily Dose and Cumulative Dose are derived per subject. Please only display once for each subject.

Protocol: GSK201893  
Population: All Treated

Listing 21  
Listing of Dose Interruptions

Treatment = xxxxxx

Center/ Subject ID	Dosing Date/ Study Day/ Dose (mg)	Primary Reason for Interruption/ Specify
xxxxx/ xxxxxx	PPD 42/ 0.80	xxxx/xxxxxxxxxx

Protocol: GSK201893  
Population: All Treated

Listing 22  
Listing of Dose Reductions

Treatment = xxxxxx

Center/ Subject ID	Dosing Date/ Study Day/ Dose (mg)	Primary Reason for Reduction/ Specify
xxxxx/ xxxxxx	ddMMyyyy/ xx/ xx	xxxx/xxxxxxxxxx

Protocol: GSK201893  
Population: All Treated

Listing 23  
Listing of Adverse Events Profiles

Treatment = xxxxxx

Center/ Subject ID	Age (Years) / Sex / Race	Preferred Term / Verbatim Text	Outcome / Onset Date / Resolve Date / Frequency / Duration	Maximum Grade / Serious / Withdrawal from Study	Time since 1st Dose / Last Dose	Action(s) taken with Treatment / Relation to GSK2820151 Treatment	Dose Limiting Toxicity?
xxxxx / xxxxxx	65 / Female / White	Nausea / NAUSEA	Resolved / ddMMyyyy / ddMMyyyy / Single Episode / xx d	Grade 4 / Yes / Yes	xx d / xx d	xxxxxxxxxxxxxxxx / XXXX	Yes

